8.2.4. Non-Parametric Analyses

8.2.4.1. Ranking

For the primary analysis of 6MWT, subjects will be ranked as follows ordered from worst to best:

1. Subjects who died prior to EEOS where time to death is used to rank earlier deaths worse than later deaths,
2. Subjects who are missing EEOS and vital status is unknown at EEOS will be ranked according to time on study drug from worst (shortest time) to best (longest time)
3. Subjects who are missing EEOS because the subject physically cannot perform the test, due to physical incapacity or other reason will be ranked according to time on study drug from worst (shortest time) to best (longest time)
4. Subjects who are missing EEOS and are known to be alive will be ranked according to time on study drug from worst (shortest time) to best (longest time)
5. Completed subject’s values will be ranked from worst (lowest distance) to best (highest distance) performance

Sensitivity analyses of the ranking will be performed by

- a) Only including ranks 1 and 5 above, and for missing reasons besides death, duration on study will be used to rank with shorter duration worse than longer duration
- b) Only including ranks 1, 3, and 5 above, and duration on study will be used to rank subjects who did not die and who are physically able to perform the test with shorter duration worse than longer duration
- c) Imputing subjects who died and who are physically not able to perform the test as zero distance in meters first, then imputing ranks for missing data using ranks 2, 4, and 5 above
- d) Imputing subjects who died or who are physically not able to perform the test (due to physical incapacity, hospitalization, or other reason) as zero distance in meters first, then imputing other missing values as the median of the observed placebo subjects at

the specified visit, then ranking all values from worst (lowest distance) to best (highest distance) performance.

The ranking paradigm with 5 levels and the ranking paradigms a and c above will also be used as sensitivity analyses for the SF-36v2 PCS score key secondary endpoint analyses.

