8.10.7.4. Time to Derived Organ Progression

The following time-to progression endpoints will be analyzed in the same manner described in Section 8.10.7.1. For all of the endpoints below, subjects who die prior to having documented disease progression will be assumed to have progressed at their date of death and subjects who discontinue due to disease progression, as reported on the ETD or EOS eCRF, will be assumed to have progressed at the date of their last contact.

- Time (months) to cardiac progression calculated as: (date first assessed with progression (Section 8.7) - the date of first study drug infusion + 1) / 30.4375. Subjects who do not experience progression will be censored at the date of last NT-proBNP assessment.
- For renal evaluable subjects, time (months) to renal progression calculated as: (date first assessed with progression (Section 8.9.1) - the date of first study drug infusion + 1) /

30.4375. Subjects who do not progress will be censored at the date of last eGFR assessment.

- Time (months) to cardiac or renal progression calculated as: (earliest date assessed as a NT-proBNP or renal progressor - the date of first study drug infusion + 1) / 30.4375. Subjects who do not progress will be censored at the minimum of the last NT-proBNP assessment date or last eGFR assessment date.

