8.10.8. Other Efficacy Analyses

8.10.8.1. Cardiac Hospitalizations

Hospitalization reason will be coded using MedDRA version 19.0. Any adverse event with a preferred term in the broad standardized MedDRA query (SMQ) definition of Cardiac Failure or in the SMQ definition of Cardiac Arrhythmias that results in hospitalization will be counted as a Cardiac Hospitalization.

Time to first cardiac hospitalization admission will be calculated in days as the date of first cardiac hospitalization admission minus the date of first study drug infusion plus 1. Subjects who do not experience an event will be censored at the date of last contact. NEOD001 will be compared to placebo using the same methods described in Section 8.10.7.1. In addition, the time to recurrent cardiac hospitalization, i.e., time to next cardiac hospitalization after the first, will be analyzed in the same manner.

The number of cardiac hospitalizations per subject over the course of the study will be summarized both as a continuous and categorical variable by treatment group. A Poisson regression model will be fit using the continuous number of cardiac hospitalizations as the dependent variable, the total time in study as the offset variable, and treatment group as a factor. The number of cardiac hospitalizations per subject will be categorized as 0, 1, and ≥ 2 . The categorical variable will be analyzed using a CMH test stratified by the randomization stratification factors. The number and percentage, with associated two-sided 95% CIs, of subjects in each category will be presented by treatment group. An ordinal logistic regression

will be performed with categorical number of hospitalizations (0, 1, and ≥ 2) as the dependent variable and factors for treatment group and randomization strata.

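### The 0, 1, ≥2 cardiac-hospitalization tests in SAP 8.10.8.1 ignore follow-up and score death without an admission as the best result, so an arm with more deaths can look better than it should (minor, exploratory)

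*SAP*

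**What the plan says.** Cardiac hospitalization is an exploratory endpoint (Protocol 3.2.4; SAP 2.3.4.8.1). It lies outside the gatekeeping sequence in SAP 8.6.

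SAP 8.10.8.1 defines the event as an adverse event in the listed cardiac failure or arrhythmia queries "that results in hospitalization will be counted as a Cardiac Hospitalization". It then plans three kinds of analysis:

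- **Categories.** "The number of cardiac hospitalizations per subject will be categorized as 0, 1, and" two or more. "The categorical variable will be analyzed using a CMH test stratified by the randomization stratification factors". The ordinal logistic regression takes the category "as the dependent variable and factors for treatment group and randomization strata".
- **Count.** A Poisson regression uses "the total time in study as the offset variable, and treatment group as a factor".
- **Time to first admission.** "Subjects who do not experience an event will be censored at the date of last contact". The methods are those of SAP 8.10.7.1: stratified log-rank test, Kaplan-Meier estimates and Cox model.

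The responder rules in SAP 8.2.2 concern best response and responses derived from a continuous variable, so they do not reach this count.

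Elsewhere the SAP treats death as a bad outcome. For organ progression (8.10.7.4), "subjects who die prior to having documented disease progression will be assumed to have progressed at their date of death". For the 6MWT (8.2.4.1), the lowest rank goes to "Subjects who died prior to EEOS where time to death is used to rank earlier deaths worse than later deaths". For SF-36v2 PCS and NIS-LL (8.2.3.1), a death is given the worst value observed at the 12-month efficacy visit.

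**The concern.** A count cannot rise after the subject has died. Someone who dies in Month 2 with no admission has a count of zero and shares a category with someone followed for 12 months without an admission. The Poisson model in the same section allows for unequal follow-up; the CMH test and the ordinal regression do not.

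If mortality differs between arms, the category odds ratio and p-values are pulled towards the arm with more deaths. A treatment that prolonged survival would be penalised because its survivors have longer to be admitted. Nothing in 8.10.8.1 combines admission and death, so no analysis there shows the reader that a low admission count may reflect early death.

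**Working it through.** **The plan's own figures.** None is given for cardiac hospitalization. The 91% power at about 130 subjects belongs to the primary endpoint. It reproduces: at 65 per arm and 50% vs 22.5%, z = (0.275·√65 − 1.96·√(2·0.3625·0.6375)) / √(0.25 + 0.1744) = 1.36, power 0.913. It has no bearing here.

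**Inputs, all assumed.** Equal admission rates λ of 0.3 or 0.6 per year in both arms; 12-month death risk q of 15% vs 5%; constant death hazard μ; one year of follow-up. Two versions: death independent of admission, and a gamma frailty with mean and variance 1 multiplying both rates.

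**Step 1: category 0 as planned, independent death.** With μ = −ln(1−q),

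P(0) = e^−(μ+λ) + [μ/(μ+λ)]·[1 − e^−(μ+λ)].

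At λ = 0.3:
- 15% deaths (μ = 0.1625): 0.6297 + 0.3514 × 0.3703 = 0.760.
- 5% deaths (μ = 0.0513): 0.7038 + 0.1460 × 0.2962 = 0.747.
- Odds ratio for category 0: (0.760/0.240)/(0.747/0.253) ≈ 1.07, favouring the arm with three times the deaths.

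**Step 2: death as the worst of four levels, same case.** Alive with no admission: 0.85 × 0.7408 = 0.630 vs 0.95 × 0.7408 = 0.704, odds ratio 0.72. Alive vs dead: (0.85/0.15)/(0.95/0.05) = 0.30. The proportional-odds fit over all four levels lies between these, at 0.65.

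**Step 3: all four scenarios.** Proportional-odds fits to the expected cell proportions (above 1 favours the higher-death arm):

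| Admissions/year | Frailty | Planned 0, 1, ≥2 | 0, 1, ≥2, death | Dead in higher-death arm scored 0 |
|---|---|---|---|---|
| 0.3 | none | 1.07 | 0.65 | 87% |
| 0.3 | shared | 1.12 | 0.67 | 80% |
| 0.6 | none | 1.09 | 0.70 | 76% |
| 0.6 | shared | 1.13 | 0.75 | 66% |

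Simulating the same scenarios gave 1.07–1.13 and 0.65–0.74. At deaths of 10% vs 5% the ranges are 1.03–1.06 and 0.80–0.86.

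**Step 4: terminal admissions.** If a share of deaths brings one cardiac admission, the planned odds ratio moves back towards and past 1. Of the shares tried (20, 30, 40 and 50%), it is first below 1 at 20% (λ = 0.3, no frailty), 30% (λ = 0.6, no frailty; λ = 0.3, frailty) and 50% (λ = 0.6, frailty).

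**Step 5: size at 65 per arm.** The standard error of the log odds ratio is about 0.34–0.43, so the shift is roughly 0.15–0.35 standard errors. A wider assumed range was also simulated (0.25–1.0 admissions per year; deaths from 5% vs 15% up to 10% vs 30%; no terminal admissions; an unstratified mean-score test standing in for the CMH test). The chance of nominal significance favouring the higher-death arm, 2.5% under no bias, was 3.4–9.5% with constant hazard and 4.3–19.2% with all deaths at 0.1 year.

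**Step 6: the companion analyses.** With independent death, the Poisson rate ratio and the cause-specific hazard ratio are both 1. With the shared frailty, the rate per unit follow-up is λ(1−q)·μ/ln(1+μ), where μ = q/(1−q). At 15% this is 0.923λ, at 5% 0.975λ, ratio 0.95: a small residual bias the same way. Kaplan-Meier with deaths censored estimates 1 − e^−λ. At λ = 0.3 that is 25.9% in both arms, while the share actually admitted is 24.0% with 15% deaths. At λ = 0.6 the figures are 45.1% and 42.0%.

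**The case against.** The case for leaving the section alone is substantial.

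- **Low stakes.** The endpoint carries no alpha, power claim or decision. This stands and sets the severity.
- **Exposure is already handled nearby.** The Poisson model with an offset is planned, and mortality is reported through overall survival (SAP 8.10.7.1) and cardiac progression-free survival (8.10.7.2). This stands. A reader might infer that the trial's hospitalization evidence is unusable; the documents do not support that. But none of these analyses corrects the category odds ratio or p-values.
- **Time to first admission.** A reader might infer that it too rewards death. It does not: a censored subject leaves the risk set and is not scored as a good outcome, and the Cox model estimates an interpretable cause-specific hazard ratio. What remains is narrower. The Kaplan-Meier estimates overstate the probability of admission when death competes, and no death-inclusive counterpart is planned.
- **Direction.** A reader might infer that the arm with more deaths will come out ahead. That is not guaranteed. Protocol 7.4.3 gives fatal acute heart failure as an example of a serious adverse event, and such an event can also be a counted admission.
- **A different question.** A scale with death on it partly re-measures mortality and includes non-cardiac death, whereas the protocol's endpoint is the frequency of cardiac hospitalizations. This is fair, and is why the death-inclusive analyses should accompany the rate and not replace it.

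**Conclusion.** The defect is in the text: two planned tests place a subject who dies without an admission in the most favourable category, with no allowance for shortened follow-up, and no other section repairs this. It also departs from how the SAP handles death for the 6MWT, SF-36v2, NIS-LL and organ progression.

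The effect is a bias and not a fixed ordering. With equal admission rates, deaths of 15% vs 5% and no terminal admissions, the planned odds ratio is about 1.07–1.13 in favour of the higher-death arm, against about 0.65–0.75 with death as the worst level. With no mortality difference there is no such bias, and it reverses if roughly 20–50% of deaths bring a terminal cardiac admission. Every rate here is an assumption. The 14.7% deaths in Protocol 1.3.2 come from blinded data in newly diagnosed subjects, a different population.

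Severity: minor. The category tests should not be read alone; the rest of the section remains interpretable.

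**What to change.** In SAP 8.10.8.1, before unblinding:

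1. Name the planned Poisson model with the time offset as the main hospitalization analysis. Define its time variable as the period in which admissions are recorded: time on study in SAP 7.1 runs to last known contact, which may fall after adverse-event collection ends.
2. Present the 0, 1, ≥2 table as description, without a test.
3. Run the CMH and ordinal logistic analyses on 0, 1, ≥2, death, with death worst, as the SAP already does for the 6MWT.
4. Keep time to first admission, state that its hazard ratio is cause-specific, and add time to first cardiac hospitalization or death.

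The cost is a few lines of SAP text and minor programming on data already collected. The downside is that items 3 and 4 add composites that include non-cardiac death, so they are reported beside the hospitalization-only rate and do not replace it.

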8.10.8.2. ECOG Performance Status, NYHA Class, Renal Stage

The number and percentage of subjects in each ECOG Performance Status ([Appendix 5](#)), NYHA class ([Appendix 6](#)), and Renal Stage ([Appendix 9](#); separately) at each visit will be presented by treatment group. Shift tables in a contingency table from baseline to worst post-baseline value, last post-baseline value, best post-baseline, and at each post-baseline visit will be provided for by treatment group.

8.10.8.3. Selected Hematological and Urine Analyte Analyses

Serum FLCs, serum PEP, and serum and urine IFE results will be summarized by treatment group using descriptive statistics at baseline, each post-baseline visit, minimum value, and maximum value. The change and percentage change from baseline will also be summarized and analyzed in the same manner described in [Section 8.8.1](#).

8.10.8.4. Disease-Related Symptoms

The number and percentage of subjects in each category of response and best response through 12 months of treatment will be presented by treatment group.

In addition, shift tables in a contingency table from baseline to worst post-baseline value, last post-baseline value, best post-baseline value, and at each post-baseline visit will be provided by treatment group.

8.10.8.5. Pharmacokinetic Analyses

Serum NEOD001 concentrations and elapsed time from the preceding NEOD001 dose will be listed. Serum NEOD001 concentrations from this study will be pooled with data from similar samples from other NEOD001 studies in a population PK analysis. Details will be described in a separate analysis plan and reported separately from the NEOD001-201 CSR.

8.10.8.6. PK/PD Analyses

PK/PD analyses will be described in a separate analysis plan and reported separately from the CSR.

9. SAFETY ANALYSES

Safety analyses will be conducted using the Safety Population.

No inferential comparison of safety endpoints will be performed, unless otherwise specified.

9.1. Extent of Exposure

The total patient exposure years (PEY) for each subject is defined as the time interval between the first dose and the last dose, inclusive, of study drug based on the subject's study drug administration information. One PEY is the equivalent of 1 subject exposed to study drug for 1 year. Two subjects who are exposed to study drug for half a year together contribute one PEY. The total PEY of a treatment group is the sum of the person exposure years of each subject in that treatment group. Duration of exposure is defined in days as the date of the last infusion of study drug – the date of the first infusion of study drug + 1.

Study drug exposure will be summarized by treatment group and will include:

- The number of subjects exposed to NEOD001, the total PEY, and duration of exposure will be summarized using descriptive statistics. This summary will be repeated for all general and special baseline subgroups defined in Section 6.
- Total Number of Infusions received will be determined for each subject by number of times the start time of drug infused is reported. If multiple infusion start times are reported on a single day, then only 1 infusion will be counted for that day. If the start time of drug infused is missing but total volume infused is greater than 0 mL, 1 infusion will be counted for that day.
- Percentage of Expected Infusions will be determined for each subject as the total number of infusions received divided by the total number of expected infusions multiplied by 100. Total number of expected infusions will be defined as the maximum of (the total number of infusions received, and the floor of ((EOS/ETD date - first infusion date + 1)/28), i.e. integer part of the function).
- Total Number of Dose Interruptions will be determined for each subject by the number of times the IV was not completed.
- Dose Strength (mg/kg) will be calculated for each subject for each visit. Total dose (mg) per infusion is not captured on the eCRF. Total dose (mg) is captured in the materials kit schedule maintained by IWRS. After unblinding, the total dose in mg will be calculated as the number of NEOD001 vials infused at each visit per IWRS, multiplied by 500 mg per vial. Total dose (mg) will be divided by the weight used to calculate total dose. If the total dose (mg) is missing but the total duration of infusion is 120 +/- 10 minutes for Month 1-Day 1 or the total duration of infusion is 60 +/-10 minutes for visits after Month 1-Day1 and IV completed is marked "Yes" then total dose will be imputed to be equal to the planned dose strength (described below). Dose strength will only be calculated where both the total dose and weight used are available. Once visit/individual specific Dose Strengths are determined, subjects will be assigned a single average Dose Strength value across all visits to be used for summary statistics in the table.

- Percent of Planned Dose Strength will be determined by dividing the actual dose strength by the planned dose strength. Calculation of actual dose strength is described above. Planned dose strength will be determined in a similar manner except the planned dose will be calculated by multiplying the reported NEOD001 dose concentration by the weight used.
- Total Number of Dose Reductions will be determined for each subject by the number of times the percent of planned dose was less than 100.

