4.3 Early Treatment Discontinuation

If the subject discontinues study drug prior to the EOS Visit, they should return for an ETD Visit 30 (\pm 5) days after their final administration of study drug as per [Section 6.2](#). If a subject fails to return for the scheduled visit, a documented effort must be made to determine the reason. If the subject cannot be reached by telephone after 2 attempts, a certified letter will be sent to the subject (or the subject's legally authorized representative, if appropriate) requesting contact with the Investigator. This information will be recorded in the study records.

If the subject discontinues study drug prior to the EOS, but is willing to continue to participate in study visits, the subject should have an ETD Visit 30 (\pm 5) days after his/her final administration of study drug (per [Section 6.2](#)) and then have assessments monthly, through Month 12 per [Appendix 13](#). The subject will not have an EOS Visit. The most important visit is the Month 12-Day 1 Visit, so if a subject is unwilling to continue monthly visits, every effort should be made for the subject to return to the clinic and complete the Month 12-Day 1 Visit on schedule. All visits after the ETD Visit should occur on schedule, that is, at the time when their visit would have occurred had they remained on study drug. Following the Month 12-Day 1 Visit, subjects will be followed for vital status per [Section 6.4](#).

Reasons for early discontinuation from study drug treatment may include, but are not limited to:

- Hematologic progression and initiation of chemotherapy is required; chemotherapy regimen should be documented on the appropriate electronic case report form (eCRF).
- Need for organ transplant or major surgery.
- A suspected NEOD001-related immunologic reaction – collect additional serum samples, if possible, during the period following the treatment stoppage to allow for the determination of the persistence of anti-NEOD001 antibodies. At a minimum, samples should be collected at the ETD Visit and 3 months after the ETD Visit, if the subject agrees to return to the clinic.
- Occurrence of an AE or clinically significant laboratory abnormality that, in the opinion of the Investigator, warrants the subject's permanent discontinuation from study drug treatment; the Medical Monitor should be notified as soon as possible of any discontinuation of study drug due to an AE.

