5.4 Dosage Adjustments

5.4.1 Withholding of Study Drug

Subjects with symptomatic orthostatic hypotension and/or systolic BP < 85 mmHg, which in the medical judgment of the Investigator would interfere with subject's ability to safely receive study drug, will have study drug withheld until the next scheduled monthly administration, but should still have all other study visit assessments completed.

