6.2 End of Study/Early Treatment Discontinuation (EOS/ETD): 30 (±5) Days AFTER Final Dose

A final visit should occur 30 (±5) days after the final administration of study drug. The assessments shown for EOS/ETD should also be conducted for any unscheduled visit (i.e., a visit not specified by the protocol) as clinically indicated or if deemed necessary.

- Concomitant medications/therapy
- Assessment of AEs
- Complete physical examination - including weight and examination of general appearance; head, ears, eyes, nose, and throat; neck; skin; cardiovascular system; respiratory system; gastrointestinal system; and nervous system. The following should be assessed: macroglossia, submandibular nodes/fullness, adenopathy, ecchymoses, liver/spleen size (palpable +/-), ascites (+/-), and edema (which should be quantified on a scale of 0-4).
- Vital signs including HR, BP, RR, and body temperature (per [Section 6.6.1.2](#)) - after subject has been at rest ≥ 5 minutes
- ECOG PS ([Appendix 7](#))
- NYHA class ([Appendix 8](#))
- NIS-LL ([Appendix 5](#)) and VASPI ([Appendix 6](#))
 - Note: NIS-LL is for all subjects with peripheral neuropathy at Screening and the addition of the VASPI is only for subjects with painful peripheral neuropathy at Screening
- SF-36v2 ([Appendix 9](#))
 - Note: Administer SF-36v2 before conducting any other assessments on the same calendar day it is administered

- KCCQ ([Appendix 10](#))
 - Note: Administer after the SF-36v2, but prior to conducting any other assessments on the same calendar day it is administered
- 6MWT ([Section 6.6.2.3](#)); collect HR and BP pre- and post-6MWT administration
 - Note: NT-proBNP should be drawn before conducting 6MWT if being performed on the same calendar day
- Echocardiogram – perform (locally) if not done within 60 days prior to visit
 - Note: To be eligible for the additional cardiac imaging analysis, the subject must have a 4-chamber view, 2-dimensional echocardiogram with Doppler
- 12-lead ECG performed in triplicate (perform centrally)
- Laboratory Assessments (central laboratory, unless otherwise noted):
 - Hematology and chemistry (including amylase and creatine kinase) per [Appendix 11](#)
 - PT/INR and PTT
 - Additional coagulation samples per [Appendix 12](#)
 - Inflammatory biomarkers per [Appendix 11](#)
 - Troponin T
 - NT-proBNP
 - Note: NT-proBNP should be drawn before conducting 6MWT if being performed on the same calendar day
 - Serum pregnancy test (WOCBP only)

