2.2. Study Design

2.2.1. Overall Study Design

[figure not shown]
This is a global, multicenter, Phase 2b, randomized, double-blind, placebo-controlled, two-arm, parallel-group efficacy and safety study of NEOD001 as a single agent administered intravenously in adults with AL amyloidosis who had a hematologic response ([Appendix 1](#)) to previous treatment for their amyloidosis (e.g., chemotherapy, ASCT) and have persistent cardiac dysfunction.

Subject screening will occur during the 28 days prior to the first administration of study drug (i.e., Month 1 Day 1 Visit). If all eligibility requirements are met, the subject will be enrolled and screening assessments will be completed. Screening assessments are listed in [Table 1](#).

Study visits will occur every 28 days based on scheduling from Month 1 Day 1. A ± 5 -day window is allowed for visits starting after Month 1. Subjects may receive up to 12 infusions of study drug. Subjects who discontinue study drug before the End of Study (EOS) Visit should have an Early Treatment Discontinuation (ETD) Visit 30 (± 5) days after their final administration of study drug. If willing, subjects may continue in the study and have monthly assessments, through Month 12, per [Appendix 12](#). Subjects who complete the study and meet the eligibility criteria will be considered for entry into a separate open-label extension study, during which subjects will receive active treatment and may receive concurrent chemotherapy.

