- For missing stop day and month – Day and month will be imputed as the last day of the year (i.e., 31 December).
- Imputed stop dates must be on or after the start date.

If a time required for calculation related to exposure is missing, the following standards will be applied:

- If start time is missing for an infusion where the volume recorded on the eCRF is greater than 0 mL then start time will be imputed as the pre-dose time of vital signs at the same visit + 1 minute. This should only be done for the first dose time within a given visit should there be more than one record.
- If stop time is missing for an infusion where the volume is greater than 0 mL then stop time will be imputed as the ‘immediately after infusion’ time of the vital signs at the same visit - 1 minute. This will only be done for the last dose time within a given visit should there be more than one record.
- If vital sign assessment times are not available, infusion start date/time is missing, and infusion stop date/time is non-missing then the start date/time will be imputed as stop date/time - 2 hours at the Month 1 Day 1 visit or as the stop date/time - 1 hour for all other visits

If vital sign assessment times are not available, infusion stop date/time is missing, and infusion start date/time is non-missing then the stop date/time will be imputed as start date/time + 2 hours at the Month 1 Day 1 visit or as the start date/time + 1 hour for all other visits. All data recorded on the case report form will be included in data listings that will accompany the CSR.

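### In SAP 9.1, Percentage of Expected Infusions scores unbroken early stopping as 100%, and the dose rows are likely to read too high below 104.2 kg and too low above it

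*SAP*

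**What the plan says.** **Infusions.** SAP 2.2.1 sets the course: "Subjects may receive up to 12 infusions of study drug", one every 28 days from Month 1-Day 1. SAP 9.1 defines the percentage as "the total number of infusions received divided by the total number of expected infusions multiplied by 100". The rule for the denominator begins: "Total number of expected infusions will be defined as the maximum of (the total number of infusions received, and the floor of". In other words, it is the larger of infusions received and the whole number of 28-day periods from first infusion to the EOS/ETD date. Protocol 6.2 fixes that date: "A final visit should occur 30 (±5) days after the final administration of study drug". Protocol 4.3 adds that a subject who stops drug but keeps attending has no EOS visit, so the ETD date is the only one available. Under Protocol 5.4.1, subjects with certain blood-pressure findings "will have study drug withheld until the next scheduled monthly administration".

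**Dose.** SAP 9.1 says mg per infusion is not on the eCRF, so "the total dose in mg will be calculated as the number of NEOD001 vials infused at each visit per IWRS, multiplied by 500 mg". Planned dose is the reported dose concentration times the weight used; the cap is not mentioned. An infusion below 100% of planned counts as a dose reduction. Protocol 5.3 gives 24 mg/kg, at most 2500 mg, with the cap applying from 104.2 kg.

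**Elsewhere.** SAP 9.1 also tabulates infusions received, duration of exposure, patient exposure years (PEY) and dose interruptions. SAP 7.1 gives Kaplan-Meier summaries of time to treatment discontinuation by arm.

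**The concern.** A percentage of expected infusions is naturally read as the share of the planned course delivered. Here the end date of the calculation is itself set by the last dose, so the row cannot show early stopping that follows an unbroken run of doses, nor a difference between arms in such stopping. It would stand at or near 100% beside infusion counts that say otherwise.

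The dose rows have a separate problem. A 24 mg/kg dose is seldom a multiple of 500 mg, so vial counts and prepared milligrams differ. The planned dose used as comparator also ignores a cap that the protocol applies. The mean mg/kg, the percent of planned and the number of dose reductions could therefore all be wrong in the clinical study report, although nothing unusual happened at the infusion visits.

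**Working it through.** **Check on the plan's own figure.** 2500 / 24 = 104.17 kg, which agrees with the protocol's 104.2 kg.

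**1. Early stopping.** Count the first infusion as Day 1. After *k* on-schedule infusions the last is on Day 28(*k*−1)+1, give or take 5 days, and EOS/ETD follows 25 to 35 days later. The latest possible EOS/ETD day is 28(*k*−1)+6+35 = 28*k*+13. The floor after dividing by 28 is therefore at most *k*, the maximum with *k* is *k*, and the row gives *k*/*k* = 100%. Running all 1331 in-window combinations for *k* = 2 to 12 gave 100% each time. For *k* = 1, ETD falls on Day 26 to 36, expected is 1, and the result is again 100%.

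| Infusions received | SAP row | Share of 12 |
|---|---|---|
| 1 | 100% | 8.3% |
| 3 | 100% | 25.0% |
| 6 | 100% | 50.0% |
| 11 | 100% | 91.7% |

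**2. Month 12 dose withheld.** The Month 11 dose falls on Day 281 ± 5. EOS timed from it falls on Day 301 to 321. 321/28 = 11.5, floor 11, so the row gives 11/11 = 100%. The missed dose counts (11/12 = 91.7%) only if EOS falls on Day 336 or later, at least 336 − 286 = 50 days after the Month 11 dose and outside the 25-to-35-day window.

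**3. One mid-course dose missed, last dose on Day 309.** EOS 25 or 26 days later is Day 334 or 335: floor 11, giving 11/11 = 100%. EOS 27 to 35 days later is Day 336 to 344: floor 12, giving 11/12 = 91.7%. If the last dose also varies over Day 304 to 314, 28 of the 121 in-window day combinations hide the missed dose. These are combinations, not probabilities.

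**4. Vials.** Assume whole vials are counted and the reported dose concentration is 24 mg/kg. Counted mg = 500 × ceiling(min(24 × weight, 2500) / 500); planned mg under the SAP = 24 × weight.

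| Weight (kg) | Prepared mg | Counted mg | SAP planned mg | Percent of planned |
|---|---|---|---|---|
| 50 | 1200 | 1500 | 1200 | 125.0 |
| 62.5 | 1500 | 1500 | 1500 | 100.0 |
| 63 | 1512 | 2000 | 1512 | 132.3 |
| 70 | 1680 | 2000 | 1680 | 119.0 |
| 80 | 1920 | 2000 | 1920 | 104.2 |
| 100 | 2400 | 2500 | 2400 | 104.2 |
| 110 | 2500 | 2500 | 2640 | 94.7 |
| 130 | 2500 | 2500 | 3120 | 80.1 |

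The documents give no weight distribution. If weights were uniform over 50 to 104 kg, the mean would be about 113% (24 × 1.129 = 27.1 mg/kg), with a range of 100% to 133%. At 45 kg it is 138.9%.

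**5. Part-given infusion (illustration).** At 70 kg, stopping after 125 of 250 mL delivers 1680 × 125/250 = 840 mg, but four vials still count as 2000 mg. The volume is available: SAP 4.3 refers to it ("If start time is missing for an infusion where the volume recorded on the eCRF is greater than 0 mL").

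**6. Rows that are not distorted.** PEY after one infusion is 1/365.25 = 0.003; after 12 on schedule it is 309/365.25 = 0.846.

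**The case against.** The strongest reply is that the plan already shows early stopping. A subject with one infusion appears as one infusion and one day of exposure. SAP 7.1 reports time to treatment discontinuation and reasons by arm, and the listings flag dose modifications. On this view the percentage is an on-treatment measure, kept apart from persistence on purpose, and it usually detects a skipped mid-course dose. That stands in large part. A reader might infer that the exposure tables as a whole overstate delivery, or that a null result would be judged only against near-perfect adherence; the documents do not support either. What does not stand is the row as an on-treatment measure: it is not labelled as one, it misses a withheld Month 12 dose when EOS is timed as the protocol requires, and one missed dose reads 100% or 91.7% according to the EOS date.

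Three other strong readings also go too far. A withheld final dose is not always missed: EOS on Day 336 or later counts it, and Protocol 6.1.2 allows a withheld dose to be rescheduled. The SAP speaks of vials infused, not opened, so whole-vial counting is an inference from kit-level IWRS data. And the dose error is not always upward, since it reverses above 104.2 kg.

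It is also fair to say that computing delivered mg from the prescribed dose gives about 100% for every completed infusion by construction, and that part-given infusions are already counted as dose interruptions. The first is a reason to keep the vial counts as a cross-check. The second does not correct the mg.

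**Conclusion.** The concern holds for specific descriptive rows of SAP 9.1 and no further.

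- **Percentage of Expected Infusions.** The fault follows from the formula and the visit timing alone. It is certain for early stopping without a skipped dose. For a withheld Month 12 dose it holds when EOS is timed from the Month 11 dose.
- **Dose Strength, Percent of Planned Dose Strength and Dose Reductions.** Below 104.2 kg the overstatement depends on whole-vial counting, and the 113% mean depends also on an assumed weight distribution. Above 104.2 kg a full capped dose reads below 100% and is counted as a reduction, provided the reported concentration is the uncapped 24 mg/kg.

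Infusion counts, duration, PEY and time to discontinuation are sound. No primary or key secondary analysis uses the affected rows. The change is still worth making before database lock, because the plan followed as written gives wrong figures and the correction rests mainly on data the SAP already uses.

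**What to change.** 1. Report infusions received divided by scheduled Day 1 infusion visits: 12, or those due up to death if earlier.
2. If the present figure is kept, label it as while on treatment and count each withheld scheduled dose as missed, including at Month 12.
3. Compute delivered mg as the dose prescribed at that visit (mg/kg times weight used, with the protocol's stated cap) × volume infused / total volume prepared across all bags. The protocol's single bag is 250 mL; Protocol 5.3 also allows several bags, so confirm that their total volume is recorded.
4. Apply the same cap to the planned dose before deriving percent of planned and counting reductions.
5. Keep IWRS vial counts as an accountability cross-check, and state whether they are whole vials.

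The cost is SAP wording and two changed derivations. The downside is that the reported percentage of infusions becomes less favourable.
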